**\*Cycle 2 Day 1 window ±4 days**

1. For women of childbearing potential only. Must be done ≤7 days prior to registration. Pregnancy testing will be repeated if patient qualifies for re-treatment.
2. If the previously cryoablated lesion no longer appears viable by imaging, DC will be injected into the previously treated region. Pevnar will be injected in the region of the first treated lesion. Patient will get DC until supply exhausted or maximum of 8 doses whichever comes first.
3. An index tumor for biopsy is identified as accessible via needle biopsy that is not the cryoablation site.
4. An index tumor lesion that is not the cryoablated or treated lesion may be biopsied if it is easily accessible or amenable to image-guided biopsy; Day 1 Cycle 1 (may be done any time prior to Day 1 Cycle 1), Day 1 Cycle 6, and Day 1 Cycle 19 (8 weeks post last dose of treatment) and at the time of disease progression. For the time point of Day 1 Cycle 1 and at time of disease progression, if excisional biopsy is done for diagnostic purposes, then remaining tissue after pathology review can be used for research studies.
5. Up to 28 days prior to registration.
6. Blood draw for immune monitoring and FACT-Lym should be collected prior to pembrolizumab administration, DC vaccine injection and Pevnar administration. Blood draw for immune monitoring and FACT-Lym during treatment period will be collected on Day 1 of Cycles 1,

- 2, 4, 6, 8, 12 and 18.
  7. Cycle 1 Day 1 order: blood for immune monitoring, leukapheresis, and pembrolizumab administration.
  8. CT or MRI does not need to be repeated if the baseline CT whole body or PET/CT is deemed adequate by study investigator.
  9. Imaging performed during active treatment period on Day 1 of Cycles 4, 8, 12, and 18. All patients who received at least 2 cycles of treatments and do not have evidence of PD should be evaluated for formal clinical response.
  10. If not enough DC, then proceed to Cycle 6.
  11. Patients with residual or progressive disease may be retreated if deemed clinically feasible. See Section 7.12. These patients will follow the same test schedule for retreatment, starting with Day 1 Cycle 2.
  12. If the baseline CBC with differential is more than 3 days from the date of leukapheresis, then a CBC with differential needs to be drawn at or within 3 days from leukapheresis.

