### 6.35 Treatment on this protocol must commence at the Mayo Clinic Rochester under the supervision of a hematologist.

### 6.36 Treatment cannot begin prior to registration and must begin $\leq 21$ days after registration.

### 6.37 Pretreatment tests / procedures must be completed within the guidelines specified on the test schedule (see Section 4.0).

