### 11.1 Response Considerations

Schedule of Evaluations: PET/CT or whole body CT scans are required at baseline for all patients. For the purposes of this study, patients should be reevaluated for disease progression at the end of each cycle. In addition to a baseline PET/CT scan, confirmatory scans should also be obtained at Day 1 of Cycles 4, 8, 12 and 18 (Section 4). During observation, CT scan should be obtained every 3 months during the first year to evaluate for disease progression.

Definitions for clinical response for patients with lymphoma are from the recently revised Cheson's et al criteria published in 2014 (Cheson, Fisher et al. 2014), derived from the original criteria published in 2007 (Cheson 2007). Lymph node measurements should be taken from the CT portion of the PET/CT, or other dedicated CT scans where applicable. Measurement of lymphadenopathy for purposes of assessing for PR will be determined by adding the sum of the products of the maximal perpendicular diameters of measured lesions (SPD). The PPD of a single node is sufficient to evaluate for PD (see Table 11.2). Measurable extranodal disease should be assessed in a manner similar to that for nodal disease. For these recommendations, the spleen is considered nodal disease. Disease that is only assessable (eg, pleural effusions, bone lesions) will be recorded as present or absent only, unless, while an abnormality is still noted by imaging studies or physical examination, it is found to be histologically and pathologically negative.

Response is based on PET/CT based on the revised 2014 Lugano Classification (Cheson, Fisher et al. 2014).

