### 11.3 Other Response Criteria:

#### 11.31 Cutaneous Response Criteria:

Lesions will be measured by physical exam and photographed to evaluate for response. Photographs of the skin lesions, marked with a ruler, will be saved/uploaded in QREADS for comparison purposes.

If all target lesions are cutaneous, then the following modified Lugano criteria will be utilized. However, if at least one target lesion is not cutaneous, then the cutaneous measurements will be grouped with the target nodal/extranodal lesions when calculating the SPD and the response criteria per section 11.2 will be utilized with reference to the table below for cutaneous definitions whenever applicable.

Modified Lugano Criteria for Cutaneous Lesions	
Response	Definition
Complete response	100% clearance of all skin lesions
Partial response	$\geq 50\%$ decrease in SPD of up to 6 target measurable cutaneous lesions and not meeting Complete response definition
Stable disease	$< 50\%$ decrease from baseline in SPD of up to 6 target measurable cutaneous lesions; no criteria for progressive disease are met

Modified Lugano Criteria for Cutaneous Lesions	
Response	Definition
Progressive disease	
≥50% increase from nadir in SPD of up to 6 target measurable cutaneous lesions;
 
New cutaneous lesions

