### 16.322 Secondary Outcome Analyses:

These analyses will include all patients meeting the eligibility criteria who have signed a consent form and have begun treatment. Analyses will include all patients enrolled in the Phase II portion of the study and analysis of each cohort separately.

16.323 Complete response (Goal 2.2.21): The response rate will be calculated, as above, in each individual cohort as supplementary to the primary analysis.

16.324 Progression free survival, treatment free survival, and duration of response (Goal 2.2.22):

Survival time is defined as the time from registration to death due to any cause. The distribution of survival time will be estimated using the method of Kaplan-Meier (Kaplan E 1958). In addition, the overall survival rate at 2 years after registration will be reported.

Treatment free survival time is defined for all evaluable patients who have achieved a response as the time from registration to next treatment or death due to any cause. The distribution of treatment-free survival will be estimated using the method of Kaplan-Meier. In addition, the disease-free survival rate at 2 years after registration will be reported.

Duration of response is defined for all evaluable patients who have achieved a PR or CR as the date at which the patient's objective status is first noted to be a response to the earliest date progression is documented. The distribution of duration of complete response will be estimated using the method of Kaplan-Meier.

16.325 Adverse Events (Goal 2.2.23): All eligible patients that have initiated treatment will be considered evaluable for assessing adverse event rate(s). The maximum grade for each type of adverse event at each evaluation will be recorded for each patient, and frequency tables will be reviewed to determine patterns. Additionally, the relationship of the adverse event(s) to the study treatment will be taken into consideration. Longitudinal analysis techniques will be utilized to determine the effect

of time on treatment adverse events.

16.326 Quality of Life (Goal 2.2.24):

Quality of life as measured using the FACT-Lym will be utilized. The assessment will be scored according to the scoring algorithm. Changes from baseline will be calculated at each assessment time points. Mean change scores at each time point will be calculated to determine if quality of life is reduced over the course of treatment. Longitudinal techniques will be employed to describe changes over time.

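### Treatment-free survival is restricted to responders but timed from registration, so the curve conditions on a later event and contains guaranteed event-free time

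*Combined protocol and SAP*

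**What the plan says.** Section 16.324 defines TFS as follows: "Treatment free survival time is defined for all evaluable patients who have achieved a response as the time from registration to next treatment or death". Death from any cause counts. The curve is to be estimated by Kaplan-Meier, and no landmark, delayed entry or other handling of the time before response is described there or elsewhere.

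The general statement for the secondary analyses, in Section 16.322, is wider: "These analyses will include all patients meeting the eligibility criteria who have signed a consent form and have begun treatment".

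For duration of response, Section 16.324 says: "Duration of response is defined for all evaluable patients who have achieved a PR or CR". The clock starts when response is first noted and stops at documented progression. The estimation sentence that follows is narrower: "The distribution of duration of complete response will be estimated using the method of Kaplan-Meier".

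Two other places set the timing. Section 4.1, footnote 9: "Imaging performed during active treatment period on Day 1 of Cycles 4, 8, 12, and 18". Section 6.36: "Treatment cannot begin prior to registration and must begin" within 21 days of registration.

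**The concern.** Membership of the TFS curve is decided by something that happens after the clock starts. A patient who dies or moves to other treatment before responding never enters it. The time each responder took to respond is nevertheless counted as follow-up during which an event could have occurred. This is guaranteed (immortal) time.

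The resulting quantity is neither TFS for the treated population nor durability once a response has been reached. In a single-arm study, a durability figure is likely to be read against outside results, so its meaning has to be clear. The shift relative to TFS from response does not shrink with sample size, and a confidence interval will not reveal it.

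The duration-of-response sentence is a smaller matter. Taken literally, the only planned curve would cover complete responders, although the endpoint has just been defined for PR or CR.

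**Working it through.** The plan gives no TFS or duration-of-response figure to reproduce. The size of the guaranteed segment follows from the visit schedule.

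**Inputs.** Cycle length 21 days (Section 4.1 notes; Section 7.111). On-treatment imaging on Day 1 of Cycles 4, 8, 12 and 18 (Section 4.1, footnote 9). First dose 0 to 21 days after registration (Section 6.36).

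**Step 1: guaranteed time per responder.** Days from first dose = (cycle − 1) × 21. Add 0 to 21 days for the lag from registration. Divide by 30.4375 for months.

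| First response at scan | Days from first dose | Days from registration | Months |
|---|---|---|---|
| Cycle 4 | 3 × 21 = 63 | 63–84 | 2.1–2.8 |
| Cycle 8 | 7 × 21 = 147 | 147–168 | 4.8–5.5 |
| Cycle 12 | 11 × 21 = 231 | 231–252 | 7.6–8.3 |
| Cycle 18 | 17 × 21 = 357 | 357–378 | 11.7–12.4 |

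These counts hold for scheduled on-treatment imaging. A ±2-day window moves each by 2/30.4375 = 0.07 month. Dose delays and unscheduled scans can also shift them. So can skin disease, for which Section 11.31 says: "Lesions will be measured by physical exam and photographed to evaluate for response". Section 11.1 adds that "patients should be reevaluated for disease progression at the end of each cycle", but that review is for progression. The optional pembrolizumab year has imaging every 3 months (Section 4.1, footnote 19), and a response first seen there would carry more guaranteed time than any row above.

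**Step 2: against TFS from first response.** If g is the time from registration to response and T the time from response to event, TFS from registration is g + T. The difference is g for every responder, and no distribution is assumed.

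**Step 3: against all-patient TFS (illustration only).** The documents give neither a TFS rate nor response times. I assume exponential event times with all-patient median m, response unrelated to outcome, and potential response at the four scans with weights w. With λ = ln 2/m, a potential response at g_k is realised only if the patient is event-free until then, so w′_k ∝ w_k·exp(−λg_k). The reported curve is S(t) = Σ w′_k·min{1, exp(−λ(t − g_k))}, solved for 0.5.

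| All-patient median (months) | 6 | 9 | 12 | 18 | 24 |
|---|---|---|---|---|---|
| All at Cycle 4, lag 0 | 8.1 | 11.1 | 14.1 | 20.1 | 26.1 |
| All at Cycle 4, lag 21 days | 8.8 | 11.8 | 14.8 | 20.8 | 26.8 |
| Mix 60/25/10/5%, lag 0 | 9.4 | 12.6 | 15.6 | 21.7 | 27.7 |
| Mix 60/25/10/5%, lag 21 days | 10.1 | 13.3 | 16.3 | 22.4 | 28.4 |

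The excess runs from 2.07 months (all at Cycle 4, lag 0) to 4.39 months (mix, lag 21 days, m = 24).

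**Step 4: scale against sampling error.** Responders number about 0.30 × 28 = 8.4 to 0.53 × 28 = 14.8. With all d events observed, a 95% interval for an exponential median is the median × exp(±1.96/√d): 0.50 to 2.00 times for d = 8, and 0.60 to 1.66 times for d = 15. The largest ratio in the table is 10.05/6 = 1.675, just above the 1.659 limit for 15 responders. Every other cell lies inside both intervals. Censoring would widen them.

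**The case against.** A responder-only TFS is a legitimate choice, the plan states its population and origin openly, and no comparison of responders with non-responders is planned, which is where guaranteed time would do most harm. All of that stands. The difficulty is only the pairing of responders with a registration start.

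Several stronger readings are tempting, but the documents do not support them.

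- *The curve must lie above all-patient TFS.* That depends on how non-responders fare. Under Section 13.2, patients with stable disease also stay on protocol treatment for 18 cycles, so a non-responder need not reach next treatment early. The excess is expected, not guaranteed.
- *The error is that time on therapy is counted as treatment-free.* Any version of this endpoint counts protocol therapy, because patients continue treatment after responding. TFS here can only mean time to next treatment. The defect is the conditioning on response.
- *No responder can have an event before response.* There may be exceptions: a first response after protocol retreatment, or during the optional pembrolizumab year, if either counts as next treatment. The plan does not say.
- *The responder restriction contradicts Section 16.322.* The specific definition in 16.324 can override the general statement.
- *PR patients are deliberately left out of the duration curve.* More probably the word *complete* is left over. Section 16.3211 has a similar slip: it describes the primary endpoint as a proportion of complete responses and then defines success as PR or CR. Goal 2.222 names duration of response without restriction.

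**Conclusion.** The point holds. Followed as written, Section 16.324 builds guaranteed event-free time into TFS: 63–84 days for a response first seen at the Cycle 4 scan, and up to 357–378 days at Cycle 18, subject to the timing caveats above. The excess over TFS from first response is exact and needs no assumption. The 2.1 to 4.4 month excess over an all-patient median rests on exponential times, response unrelated to outcome, and the chosen medians and response mixes. It is within the sampling error of a median from 8 to 15 responders in all but one illustrated case.

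A reader might infer that a reported 2-year TFS rate or the main conclusion is overstated. The plan reports no 2-year TFS rate; the 2-year disease-free rate mentioned beside TFS is not defined. The endpoints are descriptive and secondary, no test is biased, and the rule of 13 or more responses in 28 is untouched. This should be corrected before analysis, but the stakes are modest. The duration-of-response wording is a minor correction.

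**What to change.** Choose one definition of TFS in Section 16.324:

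- **Responders only, timed from the date of first documented response.** This is a wording change, removes the guaranteed segment entirely, and needs no data on non-responders.
- **All evaluable patients, timed from registration.** This removes the conditioning and matches the population in Section 16.322. First confirm that next-treatment dates are collected for non-responders. Section 13.1 sends patients who leave for other treatment to event monitoring, but Section 4.4 lists only timed follow-up, progression, death and new primary. The case report forms are not in the documents, so a form change may be needed.

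In the same edit, delete *complete* from the duration-of-response estimation sentence, so that the curve covers all patients with PR or CR, and show CR as a subset. It would also help to state what counts as next treatment (protocol retreatment, the optional pembrolizumab year), how death without progression enters duration of response, how PFS is defined, and what the 2-year disease-free rate means. These are clarifications, and the point does not depend on them.

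Sample size and the response rule do not change. The cost is a durability figure that may look less favourable.

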#### **2.22 Secondary**

2.221 Evaluate the PR and CR rate of this combination immunotherapy.

2.222 Evaluate the progression free survival, treatment free survival, duration of response, disease-free rate at 2 years, and overall survival of this combination immunotherapy.

2.223 Evaluate the safety of this combination immunotherapy.

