**4.4 Test Schedule for Event Monitoring for patients who refuse additional treatment or observation for any reason**

	Event Monitoring Phase 				
	q. 3 months during Yr 1 post-treatment; q. 4 months during Yr 2 post- treatment; q 6 months during subsequent yrs up to 4 yrs post registration until PD	At PD 	After PD q. 6 months until 4 yrs post registration	Death	New Primary
CRF					
Event Monitoring	X 	X 	X	X	At each occurrence

1. If a patient is still alive 4 years after registration, no further follow-up is required.
2. Submit copy of documentation of response or progression in the Supporting Documentation form in Medidata Rave.

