### 16.3 Phase II Portion

#### 16.31 Decision Rule

Pembrolizumab monotherapy induces an ORR of 39% in patients with

ipilimumab-naïve melanoma by central independent RECIST review. The potential activity of this agent in non-Hodgkin lymphoma (NHL) has not been tested. Similar check-point inhibitor Nivolumab (BMS) has reported ORR of 28% in B-cell NHL (ASH 2014). We estimate that Pembrolizumab may have similar single agent activities in NHL. Therefore we hypothesize that an ORR of 53% with this combination immunotherapy approach will be worthy of further testing in this disease population. We will explore if there is a difference in histologies enrolled in this study. Any specific NHL type with a clinical response defined as PR or CR in 2 or more patients may be expanded into a larger cohort for formal evaluation of ORR at the discretion of the PI and the Sponsor.

For phase II, the largest ORR where the proposed treatment regimen would be considered ineffective in this population is 30%, and the smallest ORR that would warrant subsequent studies with the proposed regimen in this patient population is 53%. The following one-stage design requires 28 evaluable patients (22 - 25 from phase II and 3 - 6 from the MTD portion of phase I provided that these patients have follicular lymphoma) to test the null hypothesis that the true ORR in this patient population is at most 30.

- 16.311 Interim Analysis: No interim analysis was planned for this study due to the following reasons: i) patients will be treated and evaluated for response up to two years from enrollment. ii) the total expected accrual time for this phase is only 18 – 24 months. If we were to conduct an interim analysis, all patients in the trial would have been accrued by the time patients in the interim analysis set have reached the primary endpoint for analysis.
- 16.312 Final Decision Rule: If 12 or fewer of 28 patients achieve overall response, then the proposed treatment is considered ineffective; and if 13 or more patients achieve overall response, then the treatment is considered promising and warrants further study.

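### Duration of response ends only at documented progression, with no rule for responders who die first, so the Kaplan-Meier curve can overstate the chance of being alive and in response

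*Combined protocol and SAP*

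**What the plan says.** Duration of response is a phase II secondary goal. Section 2.222 reads: "Evaluate the progression free survival, treatment free survival, duration of response, disease-free rate at 2 years, and overall survival of this combination immunotherapy".

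Section 16.324 sets three time-to-event rules:

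- **Overall survival.** "Survival time is defined as the time from registration to death due to any cause".
- **Treatment free survival**, for responders, is defined "as the time from registration to next treatment or death due to any cause".
- **Duration of response.** "Duration of response is defined for all evaluable patients who have achieved a PR or CR". It runs from the date the status is "first noted to be a response to the earliest date progression is documented". The estimator is then given as: "The distribution of duration of complete response will be estimated using the method of Kaplan-Meier".

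The first two count death from any cause. The third does not mention death. No other section adds death as an end event for duration of response, or gives a censoring or competing-risk rule for it. Progression free survival is in the 16.324 heading but is not defined in the text, so no defined endpoint combines progression with death. The estimation sentence also names complete response only, although the definition covers PR and CR.

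**The concern.** Kaplan-Meier needs each responder to have an event or a censoring time. When progression is the only event, a responder who dies without documented progression has no event, and ordinary practice censors that patient at death. The estimator then treats the patient as still able to progress later, at the same rate as those who remain under observation. The curve describes a setting in which nobody dies before progressing, whereas a reader will usually take it as the chance of still being alive and in response.

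The protocol foresees such deaths: the stopping rules in 16.53 include death other than from progressive disease within 30 days of the DC administration. Progression may also go undocumented. Section 11.1 schedules observation CT every 3 months in the first year. After that year the 4.5 schedule shows only the event monitoring form, and 4.4 schedules no scans. Deaths are nonetheless collected up to 4 years from registration ("If a patient is still alive 4 years after registration, no further follow-up is required").

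At stake is the reported durability of response. It is a stated secondary goal, and 16.315 lists the quality and duration of response among the considerations in any decision to terminate the study.

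**Working it through.** **1. The plan's own figure.** The only power statement (16.314) concerns response rate: 28 patients, 13 or more responses, 30% against 53%. Exact binomial:

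- P(X ≥ 13 | n = 28, p = 0.53) = 0.812, matching the stated 81%.
- P(X ≥ 13 | n = 28, p = 0.30) = 0.049, within the stated one-sided 0.05.

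Duration of response does not enter this calculation. The plan states no median, rate, event count or precision for it.

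**2. Number of responders.** At the alternative, 0.53 × 28 = 14.8, about 15. At the null, 0.30 × 28 = 8.4, about 8. One death is therefore 1/15 = 7% or 1/8 = 12.5% of the responders.

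**3. Size of the gap.** Three inputs are assumptions, not figures from the documents: constant hazards, a 2-year Kaplan-Meier value of 60% with deaths censored, and an observed share f of responders dying without progression by 2 years of 5%, 10% or 15%.

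- Progression hazard: λp = −ln(0.60)/2 = 0.2554 per year.
- Death hazard λd solves f = [λd/(λp + λd)] × [1 − exp(−2(λp + λd))].
- Alive and in response at 2 years: A = 0.60 × exp(−2λd).
- 1 minus the cumulative incidence of progression: A + f.

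| f | λd per year | Alive in response, A | Kaplan-Meier, deaths censored | Overstatement | 1 − cumulative incidence of progression |
|---|---|---|---|---|---|
| 5% | 0.0329 | 56.2% | 60% | 3.8 points | 61.2% |
| 10% | 0.0679 | 52.4% | 60% | 7.6 points | 62.4% |
| 15% | 0.1053 | 48.6% | 60% | 11.4 points | 63.6% |

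The Kaplan-Meier value lies between the other two quantities and equals neither. At f = 0 all three coincide.

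The shortcut 0.60 × (1 − d) with d = 5%, 10% or 15% gives 57%, 54% or 51%. There d is the death probability if progression could not occur. Those values of d correspond to only about 3.9%, 7.9% and 11.8% of responders actually seen to die without progression, so the shortcut understates the gap for a given observed share.

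**4. Cross-check on the time scale.** Let s be the share of response-ending events that are deaths without progression. With constant hazards, censoring them multiplies the median by 1/(1 − s): 1.05 at 5%, 1.11 at 10%, 1.25 at 20%. A simulation of 15 responders (assumed median 12 months with death counted, no other censoring) agrees in scale. Censoring one or two deaths raises the 12-month estimate by 2.4 or 4.8 points on average, and the typical median from about 12 months to 13.1 or 13.9.

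**The case against.** The strongest reply is that this is a descriptive secondary endpoint and that deaths remain visible elsewhere. Treatment free survival covers the same responders and counts death, overall survival is reported, and deaths appear in the adverse event tables. That mitigates the problem without closing it: treatment free survival starts at registration and ends at next treatment, not at progression.

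The shift is also small beside sampling error. With 15 responders and an estimate of 60%, a rough 95% half-width is 1.96 × √(0.6 × 0.4/15) = 0.248, about 25 points. That is fair, but wide intervals do not excuse an avoidable systematic error.

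Three stronger readings are tempting and should not be drawn:

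- **That the plan instructs censoring at death.** It does not say so. Censoring is the default consequence of a progression-only event under Kaplan-Meier.
- **That the bias always favours the treatment.** It runs upward only for time alive and in response, and only if at least one responder dies without documented progression. Against 1 minus the cumulative incidence of progression, the curve is too low.
- **That most lymphoma deaths after scanning stops would escape as censored.** Sections 4.4 and 4.5 collect forms and supporting documentation at progression to 4 years. For deaths from progressive disease, 10.52 accepts clinical deterioration as evidence, so many could carry a progression date. The clearly exposed group is deaths unrelated to lymphoma.

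**Conclusion.** The point holds as a defect in a secondary endpoint definition. Following 16.324 as written gives a curve that is neither the probability of being alive and in response nor the complement of the cumulative incidence of progression, and the rule is out of step with the other two definitions in its own section.

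The size cannot be found from the documents. On the stated assumptions the overstatement of being alive in response is about 4, 8 or 11 points at 2 years when 5%, 10% or 15% of responders die without progression, and zero if none do.

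A reader might infer that the trial's conclusion on efficacy is at risk. The documents do not support that. The rule in 16.312 rests on response alone, 13 or more of 28, and the test and its power are untouched. Section 16.315 names duration only as one of several considerations bearing on termination. The change is worth making because it removes a known distortion at almost no cost.

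**What to change.** In 16.324:

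1. Define duration of response, for patients with PR or CR, as the time from first response to progression or death from any cause, whichever comes first. Censor responders without an event at their last adequate disease assessment.
2. If progression alone is of interest, report its cumulative incidence with death as a competing event, as a supplement.
3. Change the estimation sentence so that it covers duration of response for PR or CR, not complete response only.

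The cost is a small edit to one paragraph. No new data are needed, because deaths are already collected to 4 years after registration. The downside is that reported durations become slightly less favourable.
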